### 6.6.1.3. Prophylactic Dose (IU/kg) and Dosing Interval (days)

The prescribed prophylactic dose and dosing frequency will be summarized descriptively for the prophylactic and ITI treatment periods.

Because dosing in this study is based on variable doses and dosing intervals, average weekly dose [REDACTED] and average dosing interval will be derived for each patient to characterize the amount of rFIXFc received for prophylaxis. Descriptive statistics will be provided using the FAS.

The average weekly [REDACTED] prophylactic dose (IU/kg) and the average prophylactic dosing interval will be based on prophylactic doses that are not separated by a bleeding episode or major surgical/rehabilitation period. Data to be included in the calculations, specifically the prophylactic doses and the total duration of prophylactic treatment, will come strictly from intervals representing two consecutive prophylactic doses (PR) during the efficacy period (see Section 5.4.2 for a description of the efficacy period). The sum of doses at PRx and the sum of interval durations (PRx+1 – PRx), will be determined across all evaluable intervals of PRx to PRx+1. As such, when an event (a bleeding episode or surgery) is encountered, the interval stops at the prophylactic dose prior to the event and continues with the first prophylactic dose after the event. The last PR dose in the study will be the end of the last interval used for these calculations.

$$\text{Average weekly prophylactic dose} = \frac{\text{Sum of doses at PR}_x \times 7}{\text{Sum of days in PR intervals}}$$

$$\text{Average daily prophylactic dose} = \frac{\text{Sum of doses at PR}_x}{\text{Sum of days in PR intervals}}$$

$$\text{Average prophylactic dosing interval} = \frac{\text{Sum of days in PR intervals}}{\text{Number of PR intervals}}$$

Prophylactic dosing will be further characterized by the number of prescribed changes in the dose and the number of prescribed changes in the dosing interval. Dose and dosing interval changes are based on recommendations made by the Investigator and may or may not reflect whatever modifications a patient actually made to his dosing regimen. The number of prescribed changes in the dose level and the number of prescribed changes in the dosing schedule will be summarized categorically (0, 1, 2, 3, 4, >4) and with descriptive statistics.

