**6.6.2.2. Compliance of Prophylactic Injections**

The compliance rate of each patient to the prescribed prophylactic and ITI dosing regimens during the efficacy period will be calculated in 2 ways: As dose compliance and as dosing interval compliance. Compliance will first be determined on a per-injection basis and then on a per-patient basis. That is, compliance for an individual dose or dosing interval will be determined and then the overall percentage of doses and dosing intervals that were in compliance will be determined for each patient.

For the purpose of evaluating compliance, the following will be considered per injection:

- The nominal dose taken compared to the nominal dose prescribed
- The actual day of treatment compared to the prescribed day of treatment

An individual dose will be considered compliant if it is within 80%-125% of the prescribed dose. An individual dosing interval will be considered compliant if the time between two prophylactic doses is within 36 hours of the prescribed dosing interval. Prescribed dose and dosing intervals are according to the Investigator. Instructions provided to the patient by the Investigator regarding dose or dosing interval changes will be used to determine compliance as of the date the information was provided to the patient.

The actual dosing intervals will be calculated as the length of time between consecutive prophylactic doses (date/time of PRx+1 – date/time of PRx), PRx+1 and PRx. The actual time between doses will be determined in minutes and converted to days as the number of minutes divided by 1440. The prescribed dosing interval will be taken from the eCRF as recorded by the Investigator. The absolute value of the difference between the actual and prescribed dosing intervals must be ≤ 1.5 day (+/- 36 hours) in order to be compliant [REDACTED]

All prophylactic injections will be used to determine prophylactic dose compliance; only the prophylactic injections used to determine the average prophylactic dosing interval (i.e., intervals not separated by a bleeding episode or surgical/rehabilitation period), as detailed in Section 5.4, will be used to evaluate prophylactic interval compliance. Dose and dosing interval compliance rates per patient will be determined as follows:

$$\text{Dose compliance rate} = \frac{\text{Number of doses taken within 80\%-125\% of prescribed dose}}{\text{Total number of doses}} \times 100$$

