where the percentage of a prescribed dose is calculated as: (nominal dose taken/prescribed dose) ×100 and the “nominal dose taken” will be determined from the nominal potency labeled on the vials used by the patient for each injection of rFIXFc.

$$\text{Dose interval compliance rate} = \frac{\text{Number of doses taken within +/- 36 hours of prescribed day/time}}{\text{Total number of intervals}} \times 100$$

A patient is considered “dose compliant” or “dosing interval compliant” if his respective rate is at least 80%.

Descriptive statistics of the percentage of nominal doses taken per patient within 80%-125% range for dosing compliance as well as frequencies for the dose compliance rate (<80%, ≥80%) will be presented for the FAS. Similarly, descriptive statistics of the percentage of doses taken per patient within ±36 hours [REDACTED] of the prescribed day as well as frequencies of the dosing interval compliance rate (<80%, ≥80%) will be presented for the FAS.

	Statistical Analysis Plan	Final v1.0
---	----------------------------------	-------------------

Based on their per-patient compliance rates for dose and dosing interval (each  $<80\%$ ,  $\geq 80\%$ ), patients will be further classified into the following mutually exclusive categories for overall compliance to their prophylactic treatment as:

- Both dose and interval compliant
- Dose compliant or interval compliant (but not both)
- Neither dose nor interval compliant

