**7.4.3. Annualized Number of Bleeding Episodes per Patient (ABR)**

The per-patient annualized number of bleeding episodes, hereafter referred to as the annualized bleeding rate (ABR), will be calculated for each patient using the following formula:

$$ABR = \frac{\text{Number of bleeding episodes during the efficacy period}}{\text{Total number of days during the efficacy period}} \times 365.25$$

The ABR will be summarized using descriptive and categorical (e.g. 0, >0-5, >5-10, >10-15, etc.) statistics for the FAS. All types of bleeding episodes (spontaneous, traumatic, and type unknown) will be included in determining the annualized number.

These tables will be presented by treatment regimen as described in Section 5.1.1.

This analysis will also be presented by the following subgroups:

- Patients with at least 50 EDs to rFIXFc within a treatment regimen
- Patients with at least 26 weeks of rFIXFc dosing within a treatment regimen
- History of bleeding (estimated frequency of bleeds in prior 3 months: 0, 1-2, 3-5 and >5)
- Patients with no major protocol deviations potentially impacting efficacy (see Section 6.5)

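### Intervals that contain a bleed are left out of average prophylactic dose, dosing interval and interval compliance but stay in the ABR, so what counts as exposure depends on the outcome

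*SAP*

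**What the plan says.** SAP 6.6.1.3 derives an average weekly dose and an average dosing interval per patient, to describe how much prophylaxis was received. It states that "the average prophylactic dosing interval will be based on prophylactic doses that are not separated by a bleeding episode" or by a major surgical/rehabilitation period. When such an event occurs, "the interval stops at the prophylactic dose prior to the event and continues with the first prophylactic dose after the event". The whole stretch from the last prophylactic dose before a bleed to the first one after it is thus left out, both its dose and its days.

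SAP 6.6.2.2 carries the restriction into interval compliance, which uses "only the prophylactic injections used to determine the average prophylactic dosing interval (i.e., intervals not separated by a bleeding episode or surgical/rehabilitation period"). Its criterion is: "An individual dosing interval will be considered compliant if the time between two prophylactic doses is within 36 hours of the prescribed dosing interval". A patient is classed as compliant "if his respective rate is at least 80" percent. Dose compliance is not restricted: "All prophylactic injections will be used to determine prophylactic dose compliance".

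The ABR in SAP 7.4.3 has as numerator the "Number of bleeding episodes during the efficacy period" and as denominator all days of that period. The efficacy period (SAP 5.4.2) is shortened for surgical/rehabilitation periods and, on prophylaxis, for gaps of more than 28 days between adjacent injections. It is not shortened for bleeds.

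**The concern.** Take two children on the same weekly regimen who both leave 14 days between two prophylactic doses. One does not bleed: his 14-day interval enters the averages and is scored non-compliant. The other bleeds late in the gap: his interval is removed from all three measures. The lapse is the same, and the bleed alone decides whether it is counted.

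Readers will set the prophylaxis ABR beside the reported dose and interval. If bleeds tend to follow overdue doses, the ABR includes those bleeds while the exposure tables omit the lapses before them, and the bleeds look like failures of a regimen taken on time.

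No other planned summary isolates this. Dose compliance compares the size of each dose taken with the size prescribed, so a skipped dose enters neither numerator nor denominator. Annualized consumption (SAP 6.6.1.4) uses all efficacy days but pools prophylactic and bleed-treatment injections. The listing of all injections and treated bleeds (SAP 12) would allow a reconstruction by hand, but it is not a summary.

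**Working it through.** The plan states no figure for this point, so there is none to reproduce. The check applies the SAP's own formulas to an assumed patient.

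**Inputs from the documents.** Regimen of 50 IU/kg every 7 days (SAP 3.1.2.2); tolerance of 36 hours and per-patient cut of 80% (SAP 6.6.2.2); ABR = bleeds / efficacy days × 365.25 (SAP 7.4.3); gap rule of more than 28 days (SAP 5.4.2.2).

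**Assumptions, not in the documents.** 364 days on prophylaxis; L lapses of 14 days, each ending in one bleed treated the day before prophylaxis resumes; all other intervals exactly 7 days.

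**Formulas.** On-time intervals = 52 − 2L. All intervals between prophylactic doses = 52 − L.

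- Current rule: only on-time intervals remain, so every L gives 7.00 days, 50.0 IU/kg per week and 100% compliance.
- All intervals: mean interval = 364/(52 − L); weekly dose = 50 × (52 − L)/52; compliance = (52 − 2L)/(52 − L).
- Overstatement of weekly dose = 52/(52 − L) − 1.

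| L | Intervals used (current / all) | Mean interval, all (days) | Weekly dose, all (IU/kg) | Overstated by | Compliance, all | ABR |
|---|---|---|---|---|---|---|
| 2 | 48 / 50 | 7.28 | 48.1 | 4% | 96.0% | 2.01 |
| 5 | 42 / 47 | 7.74 | 45.2 | 11% | 89.4% | 5.02 |
| 9 | 34 / 43 | 8.47 | 41.3 | 21% | 79.1% | 9.03 |
| 10 | 32 / 42 | 8.67 | 40.4 | 24% | 76.2% | 10.03 |

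For a child with the same lapses and no bleeds, the current rule itself gives the all-interval figures. The 80% cut is first crossed at L = 9 (L = 8 gives 36/44 = 81.8%).

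**Longer lapses.** Three of 21 days leave (364 − 63)/7 = 43 on-time intervals and 46 in all. Weekly dose is 50 × 46 × 7/364 = 44.2 IU/kg, mean interval 364/46 = 7.91 days and compliance 43/46 = 93.5%, against 50.0, 7.00 and 100% under the current rule.

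**The opposite direction.** Take 42 on-time intervals, 5 two-week lapses without a bleed, and 5 bleeds, each in a different on-time interval. The current rule drops 5 on-time intervals, leaving 37 on-time and 5 late over 37 × 7 + 5 × 14 = 329 days. Compliance is 37/42 = 88.1% and weekly dose 42 × 50 × 7/329 = 44.7 IU/kg. All intervals give 42/47 = 89.4% and 45.2 IU/kg. Here adherence is understated.

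**The 28-day boundary.** With 3 lapses of 35 days and each bleed treated on day 34, the gap between adjacent injections is 34 days. SAP 5.4.2.2 then removes 3 × 34 = 102 days, leaving 262. The ABR is 3/262 × 365.25 = 4.18 if the bleeds are still counted, which the text does not settle for a bleed that starts inside a removed gap. If each bleed is treated on day 20, the gaps are 20 and 15 days, nothing is removed, and the ABR is 3/364 × 365.25 = 3.01.

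**The case against.** The rule has a fair reason. A treatment injection can displace the next prophylactic dose, so the full interval around a bleed is not a clean measure of punctuality. This stands, and it is why the current tables should remain.

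The large figures need many lapses that end in bleeds. Protocol 5.1.1 cites as few as 3 to 4 spontaneous bleeds a year on prophylaxis, and lower rates in children on primary prophylaxis. At L = 2 the effect is small. The documents give no rate of lapses, or of bleeds after lapses. This also stands.

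A reader might infer three stronger things that the documents do not support:

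- *That the rule always flatters adherence.* It does so where bleeds follow overdue doses; the fourth step of the working shows the reverse. Nor is a child shown as fully punctual unless all his lapses end in bleeds, because lapses without a bleed are still counted.
- *That the bleed's days always stay in the ABR.* SAP 5.4.2.2 removes gaps of more than 28 days between adjacent injections, bleed treatments included.
- *That an endpoint result is biased.* Average dose and compliance are not endpoints, nothing is tested (SAP 5.1), and SAP 7.4.3 does not break the ABR down by either. The link to the ABR is made by the reader. The ABR and the inhibitor analysis are calculated the same way whether or not these intervals are dropped.

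It is also tempting to rewrite the rule so that bleed intervals are dropped when on time and scored as failures when late. That still selects on the outcome, now against adherence. With 5 bleeds in on-time intervals and 5 in lapses it gives 37/42 = 88.1%, against 42/47 = 89.4% on all intervals.

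**Conclusion.** The point holds in limited form. Three descriptive measures exclude intervals according to whether a bleed occurred, while the ABR generally keeps those bleeds and days. The direction of the distortion depends on where the bleeds fall. For the assumed weekly regimen over 52 weeks, weekly dose is overstated by about 4% with 2 two-week lapses that each end in a bleed, and by about 11% with 5. Reported compliance is then 100% in place of 96% and 89%. Misclassification at the 80% cut needs about 9 such lapses a year. In the opposite case adherence is understated by about one percentage point. All lapse counts and lengths are assumptions, and the effect scales with them. With approximately 30 patients planned, a few children could move the summaries. It merits a supplementary summary, not a change of definition.

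**What to change.** Leave the current tables as they are. In SAP 6.6.1.3 and 6.6.2.2, add the same three measures (average weekly dose, average dosing interval, interval compliance) computed on all intervals between consecutive prophylactic doses in the efficacy period, including those that contain a bleed. Exclusions for surgical/rehabilitation periods and for gaps under SAP 5.4.2.2 stay as they are.

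Report two counts beside them: the number of intervals excluded for a bleed, and how many of those were already past the prescribed interval plus 36 hours at bleed onset. Where the onset time is missing, use the first injection for the bleed. Onset is the better trigger, because a bleed that starts before the dose is overdue but is treated afterwards should not be read as a lapse.

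The prescribed interval, injection times and bleed onset times are already collected in the EPD and eCRF. The cost is a few table rows and modest programming. The added figures may be slightly less favourable than the current ones.

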#### 6.6.1.4. Consumption

The total annualized rFIXFc consumption (IU/kg) will be calculated for each patient using the following formula:

$$\text{Annualized consumption} = \frac{\text{Total IU/kg of rFIXFc during the efficacy period}}{\text{Total number of days during the efficacy period}} \times 365.25$$

The total amount of rFIXFc received will be the sum of the nominal IU/kg administered for each injection based on the units of rFIXFc as recorded from the patient's EPD and eCRF and his most recent weight.

Total annualized rFIXFc consumption per patient will be determined for the efficacy period (i.e., excluding the PK assessments and surgery/rehabilitation periods [major surgeries]). Total annualized consumption per patient will also be derived based on treatment regimen and overall.

Consumption is a secondary endpoint in this study. A description of how consumption will be summarized is described in Section 7.4.7.

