### 5.3.2. End Date and Time of the Last Treatment Regimen

The end of the last treatment regimen will be either:

- The date and time of the last rFIXFc dose for patients whose last treatment regimen was prophylaxis, ITI, or if they ended the study in a surgical/rehabilitation period.
- At 23:59 on the day of the last non-safety follow-up study visit for patients whose last treatment regimen was episodic.

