### 5.3.3. Treatment Regimen Changes

In the following sections, new treatment regimen refers to the regimen to which the patient has changed, and the previous treatment regimen refers to the regimen immediately before the new treatment regimen. The start date and time of the new treatment regimen and the end date and time of the previous treatment regimen are defined in the following scenarios:

- From an episodic regimen to a prophylactic regimen: The prophylactic regimen starts at the date and time of the first prophylactic dose in the prophylactic regimen. The episodic regimen ends 1 minute before that. If the time of the first prophylactic dose in the prophylactic regimen is not available, the prophylactic regimen will start at 00:01 on the day of the first prophylactic dose in the prophylactic regimen, and the episodic regimen will end at 23:59 on the day prior to that.
- From a prophylactic regimen to an episodic regimen: The prophylactic regimen ends at the date and time of the last prophylactic dose in the prophylactic regimen. The episodic regimen starts 1 minute after that. If the time of the last prophylactic dose in the prophylactic regimen is not available, the prophylactic regimen will end at 23:59 on the day of the last prophylactic dose in the prophylactic regimen, and the episodic regimen will start at 00:01 on the next day.
- From an episodic regimen to an ITI regimen: The ITI regimen starts at the date and time of the first ITI dose in the ITI regimen. The episodic regimen ends 1 minute before that. If the time of the first ITI dose in the ITI regimen is not available, the ITI regimen will start at 00:01 on the day of the first ITI dose in the ITI regimen, and the episodic regimen will end at 23:59 on the day prior to that.
- From a prophylactic regimen to an ITI regimen: If there is no prophylactic dose on the day of the treatment regimen change recorded in the eCRF, the ITI regimen starts at

	Statistical Analysis Plan	Final v1.0
---	----------------------------------	-------------------

00:01 on the day of treatment regimen change, and the prophylactic regimen ends at 23:59 on the day prior to the day of treatment regimen change. If there is a prophylactic dose on the day of treatment regimen change, the ITI regimen starts 1 minute after that prophylactic dose, and the prophylactic regimen ends on the date and time of that prophylactic dose.

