#### **5.4.2. Efficacy Period**

The efficacy period will be used for the evaluation of efficacy and health outcome endpoints. For a patient to have an evaluable efficacy period over the duration of study, he must have at least 1 day of treatment for an episodic regimen or at least 2 prophylactic injections for prophylactic regimens.

The start and end, and the total duration of the efficacy period for a given treatment regimen is the same as the start and end, and the total duration of that treatment regimen defined in Section 5.3.4 with the exceptions described in the following two subsections. The start of the efficacy period for each patient is the start of their first treatment regimen and the end is the end of their last.

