##### **5.4.2.1. Adjustments Due to Surgical/Rehabilitation Periods**

For analysis purposes, the efficacy period for a given treatment regimen will be adjusted for all surgical/rehabilitation periods (major and minor). The start and end of the efficacy period for a given treatment regimen are adjusted as follows:

	Statistical Analysis Plan	Final v1.0
---	----------------------------------	-------------------

- For patients on a prophylactic regimen before the start of a surgical/rehabilitation period, the efficacy period for the prophylactic regimen continues up to the last dose (for prophylaxis or bleeding) before the start of the surgical/rehabilitation period.
- For patients on the episodic regimen before the start of a surgical/rehabilitation period, the efficacy period for the episodic regimen continues up to 1 minute before the start of a surgical/rehabilitation period.
- For patients on a prophylactic regimen following the end of a surgical/rehabilitation period, the efficacy period for the prophylactic regimen starts or re-starts at the first prophylactic dose following the end of the surgical/rehabilitation period.
- For patients on the episodic regimen following the end of a surgical/rehabilitation period, the efficacy period for the episodic regimen starts or re-starts at 00:01 on the day following the end of the surgical/ rehabilitation period.

Start and end dates/times for the efficacy period for given treatment regimens and treatment regimen changes will be adjusted for each surgery (major or minor) as necessary.

For patients on a prophylactic regimen before the start of a surgical/rehabilitation period, the interval of time between the last dose before the surgical/rehabilitation period and the start of the surgical/rehabilitation period will not be attributed to the efficacy period for the prophylactic regimen. By definition, there should not be any treated bleeding episodes in this interval of time.

For patients on a prophylactic regimen following the end of a surgical/rehabilitation period, bleeding episodes that occur after discharge from a rehabilitation facility but before the next prophylactic dose will be attributed to the surgical/rehabilitation period and hence not counted towards the annualized bleeding rate (ABR).

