#### **5.4.2.2. Adjustments Due to Large Injection Intervals**

For analysis purposes, the efficacy period will also be adjusted to account for large intervals between injections resulting from missing data. A large interval is defined as >28 days between any 2 adjacent rFIXFc injections within a prophylactic treatment regimen and any such intervals will be removed from the efficacy period. The efficacy period prior to each such interval will end at the time of the first injection of this interval and restart (or start if it is the first interval of a treatment regimen) at the time of the second injection of this interval. The efficacy period will be adjusted for each identified interval that is not within a surgical/rehabilitation period. This algorithm applies only to prophylactic regimens and no adjustment for large injection intervals will be made for episodic treatment regimens.

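### Annualized consumption counts the dose that closes a prophylaxis segment but not the time it covers, which overstates use by about 2% over 50 weekly doses and by more in short or restarted segments

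*SAP*

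**What the plan says.** **Numerator.** SAP 6.6.1.4 defines consumption for each patient as IU/kg in the efficacy period, divided by days in that period, times 365.25. It is derived by regimen and overall. "The total amount of rFIXFc received will be the sum of the nominal IU/kg administered for each injection". The doses taken out are PK doses (also SAP 6.6) and those in surgical/rehabilitation periods.

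**Denominator.** SAP 5.4.2 ties the period to the regimen: the "duration of the efficacy period for a given treatment regimen is the same as the start and end" of the regimen itself, apart from adjustments for surgery and long gaps. The boundaries are as follows.

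- Switch from episodic treatment (5.3.3): "The prophylactic regimen starts at the date and time of the first prophylactic dose in the prophylactic regimen".
- End of the last regimen (5.3.2): "The date and time of the last rFIXFc dose for patients whose last treatment regimen was prophylaxis".
- Before surgery (5.4.2.1), the prophylaxis period "continues up to the last dose (for prophylaxis or bleeding) before the start of the surgical/rehabilitation period". After surgery it "starts or re-starts at the first prophylactic dose following the end of the surgical/rehabilitation period".
- Gap of more than 28 days (5.4.2.2): "The efficacy period prior to each such interval will end at the time of the first injection of this interval and restart" at the second injection.

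**First segments.** Under 5.3.1, a subject who begins on prophylaxis starts at the first rFIXFc dose, normally the Baseline IR (PK) dose, whose IU/kg is excluded. A subject who begins on episodic treatment starts 120 hours after the PK dose, so that dose lies before the period.

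**Neighbouring section.** For the average weekly dose, SAP 6.6.1.3 sums only the doses that open an interval: "The last PR dose in the study will be the end of the last interval used for these calculations".

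**The concern.** A prophylactic dose is given to cover the time that follows it. If a segment starts at a counted dose and stops at a counted dose, the last dose adds its full IU/kg to the numerator and no days to the denominator. The error always runs upward, and it recurs at each restart.

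Total annualized consumption is a secondary endpoint, summarized per patient without weighting (SAP 7.4.7). A short record counts as much as a long one and carries the largest error. SAP 7.4.3 plans ABR summaries restricted to at least 50 EDs or at least 26 weeks of dosing. SAP 7.4.7 plans no such restriction for consumption, so short records go straight into its mean and maximum.

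**Working it through.** The documents give no consumption figure to reproduce, so the SAP formula is applied to a regular schedule.

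**Inputs.** Dose D = 50 IU/kg and interval 7 days, the recommended starting regimen (SAP 3.1.2.2), used only as illustration. The number of doses n in the segment is an assumption. Completers reach at least 50 EDs, and SAP 5.4.2 accepts as few as 2 prophylactic injections.

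**Are boundary doses inside the period?** Yes, on the SAP's own drafting. Where it wants a dose outside a period, it sets the end one minute ahead of that dose. It does this for the episodic regimen at a switch (5.3.3) and for the surgical period before the next regular prophylactic dose (5.4.3). The prophylaxis boundaries have no such offset.

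**One segment, counted dose at both ends.**

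- As written: nD / (7(n-1)) × 365.25
- Matched to time: (n-1)D / (7(n-1)) × 365.25 = 50/7 × 365.25 = 2,608.9 IU/kg/year
- Ratio: n/(n-1), an excess of 1/(n-1)

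| n | As written (IU/kg/year) | Excess |
|---|---|---|
| 50 | 2,662.2 | 2.0% |
| 26 | 2,713.3 | 4.0% |
| 20 | 2,746.2 | 5.3% |
| 10 | 2,898.8 | 11.1% |
| 5 | 3,261.2 | 25% |
| 2 (evaluability floor) | 5,217.9 | 100% |

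**Restarts.** With k such segments the ratio is n/(n-k). For n = 50, two segments give 2,717.6 (+4.2%) and three give 2,775.5 (+6.4%).

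**Subject who begins on prophylaxis, PK dose first and excluded.** Of 50 doses including the PK dose, one unbroken segment has 49 counted doses over 49 intervals: 2,608.9, no excess. With one split there are 49 counted doses over 48 intervals: 2,663.3 (+2.1%).

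**Bleed doses.** Add four bleed-treatment doses of 50 IU/kg to the 50-dose segment. The result is 54 against 53 doses over the same 343 days: 2,875.1 against 2,821.9, and 54/53 = +1.9%.

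**Overall column.** Assume a switcher with 180 episodic days and three bleed doses of 50 IU/kg.

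- 10 prophylactic doses: 13 × 50 / 243 × 365.25 = 977.0, against 901.9 without the closing dose (+8.3%).
- 47 prophylactic doses: 1,819.0 against 1,782.6 (+2.0%).

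**Comparison with 6.6.1.3.** For 50 equal weekly doses with no bleeds or surgery, 6.6.1.3 returns 50.0 IU/kg per week. The 6.6.1.4 formula implies 50 × 50/49 = 51.0.

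**Boundaries where the effect is absent.**

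- If prophylaxis changes to ITI on a day without a prophylactic dose, the segment ends at 23:59 the day before (5.3.3), so time after the last dose is counted.
- At a change from prophylaxis to episodic treatment, the days after the closing dose count as episodic. The prophylaxis figure is overstated, but the overall figure is not.

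**The case against.** The strongest reply is that total drug given over observed time is a recognizable convention, and Protocol 16.2.3 annualizes consumption in the same way as bleeds. The outputs of 6.6.1.3 and 6.6.1.4 also measure different things. The first uses only prophylactic intervals free of bleeds and major surgery, and the second measures all use. A difference between them would not by itself show an error. That is fair. The case rests on the boundary rules, and 6.6.1.3 shows only that a matched convention is already in use.

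The size is also modest. A completer on weekly dosing is off by about 2%. The doubling occurs only at the two-injection floor, and the documents do not show how many subjects come near it. Medians are reported, nothing is tested, and the primary endpoint is untouched. All of this stands.

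A reader might infer that the tables will make switchers look like heavier users than subjects who begin on prophylaxis. The documents do not support that. SAP 5.1.1 groups patients by regimens ever received, the prophylaxis column pools both kinds of subject, and no output compares them. Nor is the effect confined to switchers, because any subject's re-opened segment has it.

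The protection of subjects who begin on prophylaxis has limits. Protocol 7.3.1 lets the Baseline IR Visit be delayed for bleeding, so the first dose can be a counted bleed dose. SAP 6.6.1.4 also describes its period as excluding PK assessments, which could be read as removing the time as well as the dose.

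**Conclusion.** The point holds as a small, directional flaw in one secondary endpoint. A prophylaxis segment with a counted prophylactic dose at both ends has n doses over n-1 intervals. Its consumption is overstated by about 1/(n-1): 2% at 50 weekly doses, 5% at 20, 11% at 10, and more only in very short segments. Splits add to this, and bleed-treatment doses dilute it.

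The figures assume equal doses and intervals, and boundary doses that count as inside the period. They also assume that the PK dose opens the first segment of a subject who begins on prophylaxis, with its time kept. Under those assumptions that first segment is already about right. The flaw warrants a clarification. It does not cast doubt on the trial's conclusions.

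**What to change.** In SAP 6.6.1.4, state the rule by segment:

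- Where a prophylaxis segment opens with a counted dose and closes at a prophylactic dose, leave the closing prophylactic dose out of the numerator, consistent with 6.6.1.3. Apply this at the end of the regimen and at surgery and long-gap splits.
- Keep every bleed-treatment dose, including one that closes a segment.
- Make no omission where the opening dose is an excluded PK dose, or where the segment does not end at a dose.
- In the overall figure, make no omission at a change from prophylaxis to episodic treatment, because the following days are counted.

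Dropping every closing dose would be wrong. A segment opened by the PK dose would then have n-2 counted doses over n-1 intervals: 48/49, or -2.0%, at n = 50, and 8/9, or -11.1%, at n = 10. Counting the PK dose to repair this would conflict with SAP 6.6. First segments in which a bleed dose precedes the PK dose need an explicit programming decision.

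The cost is a few lines in the SAP, a little programming and slightly lower reported consumption. Data collection and treatment rules do not change.
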